12.6 Statistical Analysis Plan

Patient demographics, baseline disease characteristics and prior treatment therapy will be summarized using descriptive statistics. For continuous variables, descriptive statistics such as number, mean, standard deviation, standard error, median (range) etc. will be provided. For categorical variables, patient counts and percentages will be provided.

CR rate after PolaR-ICE salvage therapy will be estimated by the proportion of response-evaluable patients achieving CR after 2 cycles of salvage therapy, along with the 95% exact binomial confidence interval. ORR after PolaR-ICE salvage therapy will be similarly estimated. PFS and OS will be estimated using the product-limit method of Kaplan and Meier along with the Greenwood estimator of standard error; 95% confidence interval will be constructed based on log-log transformation. Median PFS/OS will be estimated when

available. Observed toxicities of PolaR-ICE salvage therapy and Pola single-agent consolidation therapy will be summarized by type (organ affected or laboratory determination such as absolute neutrophil count), severity, and attribution.

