12.1.2 Phase 2 design

The Phase 2 portion of the study adopts a two-stage design. Patients who were enrolled during the safety lead-in portion at the final dose level deemed tolerable for Phase 2 will also be included in the Phase 2 response evaluation if they are evaluable for response.

At the first stage, 20 patients will be enrolled. If <8 complete responses are seen, the accrual will be terminated. If at least 8 patients achieve a complete response, the trial will continue to the second stage. At the second stage, 20 additional patients will be entered. At the end of stage 2, if 21 or more patients out of the total 40 patients experience a complete response, the combination will be considered worthy of further study. If <21 patients experience a complete response then no further investigation of the combination is warranted.

The 2-stage design aims to differentiate between the null hypothesis (disappointing rate) of 40% CR rate and an alternative hypothesis (promising rate) of 60% CR rate. The null hypothesis of 40% CR rate is based on a large randomized study comparing R-ICE with R-DHAP (rituximab, dexamethasone, cytarabine, cisplatin) as salvage regimen followed by ASCT for relapsed/refractory DLBCL.[8] Similar complete

response rates were observed after 3 cycles of R-ICE (37%, n=197) vs. 3 cycles R-DHAP (40%, n=191). Therefore, we would consider a 40% CR rate a discouraging rate and 60% a promising CR rate for this regimen to merit further study. The design has a 1-sided type I error of 7.3% and a power of 87%. The expected sample size under the null hypothesis is 31.7, and the design has a 42% chance of early termination after Stage I if the true CR rate is 40%.

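### Section 12.6 estimates the CR rate as if the design had one stage: the raw proportion is biased slightly downward, and the 95% interval is not at the level of the 21/40 rule (minor)

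*Combined protocol and SAP*

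**What the plan says.** Section 12.1.2 sets the decision rule.

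- Stage 1: "At the first stage, 20 patients will be enrolled", and "If <8 complete responses are seen, the accrual will be terminated".
- Stage 2: "At the second stage, 20 additional patients will be entered", and "if 21 or more patients out of the total 40 patients experience a complete response, the combination will be considered worthy of further study".
- Hypotheses: a "null hypothesis (disappointing rate) of 40% CR rate and an alternative hypothesis (promising rate) of 60% CR rate".
- Operating characteristics: "The design has a 1-sided type I error of 7.3% and a power of 87" percent. Also, "The expected sample size under the null hypothesis is 31.7, and the design has a 42% chance of early termination after Stage I" at a true rate of 40%.

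The synopsis and section 2.3 repeat the count rule.

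Section 12.6 gives the whole planned analysis of the primary CR rate: the proportion of response-evaluable patients "achieving CR after 2 cycles of salvage therapy, along with the 95% exact binomial confidence interval". It does not mention the stage 1 stop, a p-value, a limit at the 7.3% level, or how the interval relates to the 21/40 rule. It does not state how the interval is constructed.

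**The concern.** After a two-stage design with a futility stop, the raw proportion is no longer unbiased. Trials that start badly stop at 20 patients and keep their low estimate. Trials that start well go on, and the second stage pulls their estimate back toward the true rate. The average is therefore too low.

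Separately, a two-sided 95% interval tests at one-sided 2.5%, which is stricter than the 7.3% rule. Some trials that pass will then report an interval that still includes the 40% rate the plan calls disappointing, with nothing in 12.6 to explain how the two fit together.

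At stake are the accuracy of the published CR rate, chiefly for a trial that completes and fails, and the reading of a borderline pass. If the relation is not stated beforehand, emphasis could fall on the rule or on the interval once the count is known.

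**Working it through.** **Inputs.** From 12.1.2: n1 = 20, continue if X1 ≥ 8, n2 = 20, pass if S = X1 + X2 ≥ 21, p0 = 0.40, p1 = 0.60. From 12.2: non-evaluable patients are replaced, so the denominators are taken as exactly 20 and 40. Assumption: the exact binomial interval is two-sided Clopper-Pearson.

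**Step 1. Reproduce the plan's figures.** P(pass | p) = Σ over x = 8..20 of b(20, x, p) × P(Bin(20, p) ≥ 21 − x).

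- At p = 0.40: 0.0731 (plan 7.3%).
- At p = 0.60: 0.8659 (plan 87%).
- P(stop | 0.40) = P(X1 ≤ 7) = 0.4159 (plan 42%).
- E(N | 0.40) = 20 + 20 × (1 − 0.4159) = 31.68 (plan 31.7).

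All four agree. A single-stage rule of 21/40 would give 0.0744 and 0.8702, so the plan's figures are the two-stage ones.

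**Step 2. Bias of the raw proportion.** The estimate is X1/20 if stopped and S/40 if continued. At p = 0.40, E(X1; stop) = 2.4646, so E(X1; continue) = 8 − 2.4646 = 5.5354. The second stage contributes 8 × 0.5841 = 4.673. Then E = 2.4646/20 + (5.5354 + 4.673)/40 = 0.1232 + 0.2552 = 0.378, a bias of −2.2 points. The same sum gives 0.488 at p = 0.50 (−1.2) and 0.597 at p = 0.60 (−0.3).

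**Step 3. Unbiased estimate.** The uniformly minimum variance unbiased estimate is X1/20 if stopped. If continued it is Σ C(19, x−1) C(20, S−x) / Σ C(20, x) C(20, S−x), with x running from 8 to 20 subject to 0 ≤ S − x ≤ 20.

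| CRs of 40 | Raw | Unbiased | Difference (points) |
|---|---|---|---|
| 16 | 40.0% | 44.8% | 4.8 |
| 18 | 45.0% | 47.5% | 2.5 |
| 21 | 52.5% | 53.0% | 0.5 |
| 22 | 55.0% | 55.3% | 0.3 |

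Root mean squared error, raw against unbiased, in points: 9.6 against 10.0 at a true 40%, 9.7 against 9.1 at 50%, and 8.4 against 8.1 at 60%.

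**Step 4. Intervals and the rule.** The two-stage limits invert P(continue and S ≥ s).

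| CRs of 40 | Ordinary 95% | Two-stage 95% | Two-stage p at 40% | Two-stage lower limit at the design's alpha |
|---|---|---|---|---|
| 21 | 36.1–68.5% | 36.2–68.6% | 0.0731 | 40.0% |
| 22 | 38.5–70.7% | 38.5–70.8% | 0.0389 | 42.4% |
| 23 | 40.9–73.0% | 40.9–73.0% | 0.0189 | 44.8% |

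The 95% interval first excludes 40% at 23, so 21 and 22 are the discordant counts. Adjusting the 95% interval for the two stages moves these limits by about 0.1 point and leaves both counts discordant. The confidence level is what causes the mismatch. The two-stage calculation matters only for exact agreement at the boundary: at one-sided 7.3%, the ordinary exact lower limit for 21/40 is 39.9%, just under the null. The two-stage limit is 40.0% at the unrounded alpha of 7.305%.

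**Step 5. How often.** P(S = 21 or 22) is 0.0342 + 0.0200 = 5.4% at a true 40%, 0.1160 + 0.1018 = 21.8% at 50%, and 0.0769 + 0.1013 = 17.8% at 60%. As a share of passing trials this is 5.4/7.3 = 74% at 40% and 17.8/86.6 = 21% at 60%.

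**Step 6. Coverage.** The ordinary 95% interval covers 96.5% at a true 40% and 95.1% at 60%. Its minimum over a fine grid of rates is 94.7%.

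**The case against.** The strongest reply is that nothing is broken. The decision is a count, stated the same way in the synopsis, 2.3 and 12.1.2. Section 12.6 plans an estimate and makes the interval no part of the decision. A 95% interval beside a more lenient phase 2 screening rule is a common convention, and the two answer different questions. When the true rate is 40%, an interval containing 40% is correct and a useful warning that the evidence is modest. The bias is downward, so it cannot flatter the regimen. It is about half a point in trials that only just pass, inside an interval about 32 points wide. The larger shifts, at 16/40 and 18/40, belong to trials that fail either way.

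All of that stands, and it limits the point to reporting. It does not remove it. A completed negative trial would still publish a CR rate up to several points below the unbiased one, and 12.6 does not tell the reader how to read a pass at 21 or 22.

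A reader might go further and infer that the plan contradicts itself, that its error rates are wrong, or that ignoring the futility stop makes the interval unreliable or causes the discordance. The documents do not support these readings. The stated type I error and power reproduce, coverage is near nominal, and a two-stage 95% interval leaves the same two counts discordant.

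**Conclusion.** The point holds as a minor gap in reporting and interpretation. The raw proportion planned in 12.6 understates the CR rate on average by 2.2 points at a true 40%, falling to 0.3 at 60%. The shift is material only in completed trials that miss 21/40. At 21 or 22 CRs the trial passes while its 95% interval contains 40%, purely because the interval works at one-sided 2.5% and the rule at 7.3%. No decision, error rate or sample size changes.

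This rests on reading the interval as two-sided Clopper-Pearson and on exactly 20 and 40 evaluable patients at the two analyses.

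**What to change.** Amend 12.6 in three ways:

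1. Report the uniformly minimum variance unbiased estimate for the two-stage design beside the raw proportion.
2. Report the two-stage exact p-value against 40%, with the matching one-sided lower limit at the design's unrounded alpha (40.0% at 21/40, 42.4% at 22/40).
3. Keep the 95% exact interval, name its construction, label it descriptive, and state that the decision rests on the count rule alone.

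A two-stage 95% interval is optional. At the passing counts near the boundary it moves the limits by about 0.1 point and does not remove the discordance.

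The cost is a few sentences and a few lines of code, with no patients and no design change. The downside is one more estimate to explain, with a somewhat larger root mean squared error than the raw proportion if the true rate is 40% or lower.

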12.7 Analysis of the exploratory objectives

For the exploratory objectives, descriptive statistics will be used to summarize the correlative study measures such as ctDNA measures or other biomarkers. For continuous variables, number, mean, standard deviation, standard error, median (range) etc., will be provided. For categorical variables, patient counts and percentages will be provided. Changes in these measures before, during, and after treatment (when measured) will also be summarized by descriptive statistics and tables/plots.

Various statistical analyses will be used to explore the association between these correlative measures (at different time points and the changes over time, when measured) with clinical outcomes. For the exploratory correlation of these endpoints with response, analyses comparing groups of participants defined by response may be conducted by various two sample tests such as two-sample t-test or Wilcoxon rank sum test for the continuous correlative endpoints, or Chi-square test/Fisher's exact test for the categorical correlative endpoints. For the exploratory correlation of these endpoints with survival outcomes, survival analysis techniques such as Log rank test will be considered. Appropriate regression models will also be considered which examine the association of these correlative measures with disease outcome adjusting for other disease risk factors, such as logistic regression for response and Cox proportional hazards models for survival outcomes. All these analyses are exploratory in nature and are intended to generate hypotheses that may be validated in larger studies; no multiple comparison adjustments will be made in these exploratory analyses.

13.0 DATA HANDLING, DATA MANAGEMENT, RECORD KEEPING

13.1 Source Documents

Source documents are original documents, data, and records (e.g., medical records, pharmacy dispensing records, recorded data from automated instruments, laboratory data) that are relevant to the clinical trial. The Investigator or their designee will prepare and maintain adequate and accurate source documents. These documents are designed to record all observations and other pertinent data for each patient enrolled in this clinical trial. Source documents must be adequate to reconstruct all data transcribed onto the case report forms.

13.2 Data Capture Methods and Management

Data for this trial will be collected using City of Hope's electronic capture system (EDC) that is compliant with 21 CFR Part 11.

Study personnel will enter data from source documents corresponding to a subject's visit into the protocol-specific electronic Case Report Form (eCRF).

13.3 Case Report Forms/Data Submission Schedule

The Investigator is responsible for all information collected on subjects enrolled in this study. All data collected during the course of this study must be reviewed and verified for completeness and accuracy by the Investigator. All case report forms must be completed by designated study personnel. The completed case report forms must be reviewed, signed and dated by the Investigator or designee in a timely fashion.

All data will be collected using electronic data collection, stored as indicated in Section 13.2, and will be submitted according to the timelines indicated in Table 13.3.

Table 13.3 Data Submission Schedule

Form	Submission Timeline
Eligibility Checklist	Complete prior to registration
On Study Forms	Within 14 calendar days of registration
Baseline Assessment Forms	Within 14 calendar days of registration
Treatment Forms	Within 10 calendar days of treatment administration
Adverse Event Report Forms	Safety Lead-in Salvage Cycles 1 & 2: Within 7 calendar days of
	AE assessment/notification
	Safety Lead-in remaining cycles and Phase 2: Within 10
	calendar days of AE assessment/notification
Response Assessment Forms	Within 10 calendar days of the response assessment
Other Assessment Forms (concomitant	Within 10 calendar days of the assessment
medications)	
Off Treatment/Off Study Forms	Within 10 calendar days of end of treatment/study
Follow up/Survival Forms	Within 14 calendar days of the follow up activity

13.4 Regulatory Records

The Investigator will maintain regulatory records, including updating records in accordance with Good Clinical Practice guidelines and FDA regulations.

14.0 REPORTING OF ADVERSE EVENTS, UNANTICIPATED PROBLEMS & OTHER EVENTS OF INTEREST

The research team is responsible for classifying adverse events (AEs) and unanticipated problems (UPs) as defined in the relevant regulations and reporting to all applicable parties, including but not limited to the COH IRB, DSMC, Food and Drug Administration (FDA), National Institutes of Health (NIH) and other collaborators, e.g., pharmaceutical companies. The research team is responsible for the continued monitoring and tracking of all AEs in order to ensure non-reportable events are reviewed and monitored and do not rise to a reporting level.

14.1 Assessment of Adverse Events

The site Investigator will be responsible for determining the event name, and assessing the severity (i.e., grade), expectedness, and attribution of all adverse events as applicable per the City of Hope Clinical Research Adverse Event and Unanticipated Problem policy (available from the DCC). Adverse events will be characterized using the descriptions and grading scales found in NCI CTCAE v5.0. A copy of the scale can be found at:

https://ctep.cancer.gov/protocoldevelopment/electronic_applications/ctc.htm.

The following definitions will be used to determine the causality (attribution) of the event to the study agent or study procedure.

Unrelated – The event is clearly NOT related to study treatment, and is clearly related to other
factors such as the participant's clinical state, other therapeutic interventions, or concomitant
medications administered to the participant.

- Unlikely The event is unlikely related to the study treatment, and is most likely related to other
 factors such as the participant's clinical state, other therapeutic interventions, or concomitant
 drugs.
- **Possible** The event may be related to study treatment, as it follows a reasonable temporal sequence from the time of drug administration, but could have been produced by other factors such as the participant's clinical state, other therapeutic interventions, or concomitant drugs.
- **Probable** The event is most likely related to the study treatment, as it follows a reasonable temporal sequence from the time of drug administration and a known response pattern to the study drug, and is unlikely related to the participant's clinical state, other therapeutic interventions, or concomitant drugs.

Definite – The event is clearly related to the study treatment, as it follows a reasonable temporal sequence from the time of drug administration and a known response pattern to the study drug, and is not reasonably explained by other factors such as the participant's condition, therapeutic interventions, or concomitant drugs.

14.2 Adverse Events of Special Interest (AESI)

AESIs are a subset of events to monitor of scientific and medical concern specific to the study, for which ongoing monitoring and rapid communication by the Investigator to the Sponsor and industry partner is required. Such an event might require further investigation in order to characterize and understand it. Depending on the nature of the event, rapid communication by the trial Sponsor to other parties (e.g., regulatory authorities) may also be warranted.

14.2.1 Potential Drug-induced Liver Injury (DILI)

A potential DILI includes an elevated ALT or AST in combination with either an elevated bilirubin or clinical jaundice, as defined by Hy's Law:

- Treatment-emergent ALT or AST $> 3 \times$ ULN in combination with total bilirubin $> 2 \times$ ULN
- Treatment-emergent ALT or AST > 3 × ULN in combination with clinical jaundice

14.2.2 Suspected transmission of an infectious agent by the study drug

Any organism, virus, or infectious particle (e.g., prion protein transmitting transmissible spongiform encephalopathy), pathogenic or non-pathogenic, is considered an infectious agent. A transmission of an infectious agent may be suspected from clinical symptoms or laboratory findings that indicate an infection in a patient exposed to medicinal product. This term applies only when a contamination of the study drug is suspected.

14.2.3 Tumor lysis syndrome (TLS)

TLS of any grade (irrespective of causality).

14.2.4 Secondary Malignancy

A secondary malignancy is a cancer caused by treatment for a previous malignancy (e.g., treatment with investigational agent/intervention, radiation or chemotherapy). A secondary malignancy is not considered a metastasis of the initial neoplasm.

14.3 Pregnancies

14.3.1 Female participants:

Pregnancies and suspected pregnancies (including a positive pregnancy test regardless of age or disease state) of a female participant occurring after the participant receives the first dose of protocol therapy up to 90 days post-last dose of polatuzumab vedotin are considered immediately reportable events. Protocol therapy is to be discontinued immediately. The pregnancy, suspected pregnancy, or positive pregnancy test must be reported to the Study PI and the DCC immediately within 24 hours of awareness (Section 14.6). The female subject may be referred to an obstetrician-gynecologist (preferably one with reproductive toxicity experience) or another appropriate healthcare professional for further evaluation.

The Investigator should make every effort to follow the female participant until completion of the pregnancy per institutional policies, and should notify the Study PI.

Abnormal pregnancy outcomes, neonatal deaths that occur within 28 days of birth, and any congenital anomaly/birth defect should be reported as an SAE per expedited reporting guidelines.

Any infant death after 28 days that the Investigator suspects is related to the in utero exposure to protocol therapy should also be reported as an SAE per expedited reporting guidelines.

Follow guidelines in Section 14.8 for reporting to Genentech.

14.3.2 Male participants:

If a female partner of a male participant becomes pregnant, the male participant should notify the Investigator, and the pregnant female partner should be advised to call their healthcare provider immediately.

Pregnancy of a male participant's partner occurring after the participant receives the first dose of protocol therapy up to 90 days post-last dose of polatuzumab vedotin are considered immediately reportable events.

The Investigator should make every effort to follow the outcome of the pregnancy per institutional policies, and should notify the Study PI.

Follow guidelines in Section 14.8 for reporting to Genentech.

14.4 Post-Study Adverse Events

Any SAE occurring after a subject has completed or discontinued study participation if attributed to prior polatuzumab vedotin should be expeditiously reported to Genentech (see Section 14.8). If the investigator should become aware of the development of cancer or a congenital anomaly in a subsequently conceived offspring of a female subject, including pregnancy occurring in the partner of a male subject, this should be adequately reported as an SAE to Genentech.

14.5 Routine AE Collection and Reporting Guidelines

Routine recording of adverse events will occur via data entry into the study eCRF. Adverse events will be collected from the signing of informed consent until ending study participation, except those occurring between the end of salvage visit and the start of consolidation for subjects proceeding to HCT. Adverse events will be monitored by the Protocol Management Team (PMT). AEs reported through expedited processes (e.g., reported to the IRB, DSMC, FDA, etc.) must also be reported in routine study data submissions.

AEs recorded in the eCRF include:

- The highest grade of any toxicity for each cycle during protocol treatment and for the period of safety follow-up after end of treatment
- o For Cycles 1 and 2 only, all Grade ≥2 AEs (highest grade or not) will also be collected
- o All SAEs

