- d. Patients must meet the criteria to receive Consolidation Pola within timelines specified in Section 5.7.1. Patients who received 2 cycles of PolaR-ICE during Salvage will receive 4 cycles of Pola Consolidation. Patients who received 3 cycles of PolaR-ICE during Salvage will receive 3 cycles of Pola Consolidation. The maximum number of Pola-containing cycles of therapy is 6.
- e. Activities to be performed within 72 hours prior to initiation of the cycle.
- f. Evaluations performed within 14 days prior to start of Consolidation Day 1 may serve as Day 1 evaluations.
- g. Day 15 assessments have a ± 7 day window.

- h. End of salvage visit to occur within 30 days from last dose. Patients eligible for AHCT will then proceed to AHCT.
- i. The Safety 30 days post-last dose assessments to occur 30 (±7) days post-last dose or, if > 30 days elapsed since last dose, within 7 days after decision to end treatment. Expedited reporting will occur during this period. Safety follow-up may be extended until resolution/ stabilization of reportable AEs.
- j. For participants yet to progress, Active Follow-up will occur at 12 months (± 30 days) and 24 months (± 30 days) from the start of treatment until progression or the initiation of a new anti-lymphoma therapy.
- k. Participants who end Active Follow-up will enter Survival Follow-up. Survival assessment to occur bi-annually or as requested by the Study PI via medical record review, review of social security registry, or telephone call.
- I. Standard physical exam includes weight.
- m. Vital signs: heart rate, blood pressure, respiration rate, and temperature.
- Women of child bearing potential: Pregnancy serum or urine test. For the screening time point, pregnancy test must be performed within 7 days prior to start of protocol therapy.
- o. Screening laboratory assessments to be performed within 14 days prior to start of protocol therapy.
- p. Serum chemistry panel to include: glucose, Blood Urea Nitrogen (BUN), creatinine, uric acid, total protein, albumin, magnesium, bicarbonate, calcium, inorganic phosphorous, sodium, potassium, chloride, total bilirubin, alkaline phosphatase, ALT, AST, and LDH.
- Refer to Section 9.1.2.
- r. Archival tumor tissue to be submitted post-enrollment. Note: If unavailable, exceptions may be granted by the Study PI. Refer to Section 9.1.1.

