11.2 Primary Endpoint(s)

Unacceptable Toxicity: defined as any of the following events occurring during the first 2 cycles of treatment that is at least possibly related to study treatment:

- Any Grade 3 or higher non-hematologic toxicity that does not resolve to Grade 1 or better within 7 days with the exception of:
 - Grade 3 asymptomatic laboratory abnormalities, including lipase or amylase, that are not clinically relevant, not requiring hospitalization or delay of treatment
 - Grade 4 isolated electrolyte abnormalities that are not clinically significant including, but not limited to, hypo-or hyperglycemia, hypo-or hypernatremia, hypo-or hyperkalemia, hypo-or hypermagnesemia, or hypo-or hypophosphatemia, that resolve, with or without intervention, to Grade 2 in less than 72 hours
 - Grade 3 nausea, vomiting, or fatigue controlled with supportive measures (and does not require hospitalization, TPN, or tube feeding)
 - Grade 3 infusion reaction that resolves with appropriate management to Grade 1 or better within 24 hours
 - Alopecia of any grade
- Any Grade 3 or 4 thrombocytopenia associated with clinically significant bleeding.
- Any Grade 4 neutropenia (despite the use of growth factor) or grade 4 thrombocytopenia (without clinically significant bleeding) that lasts > 21 days.
- Any Grade 4 anemia unexplained by underlying disease.
- Any treatment-related toxicity that delays cycle 2 treatment for >2 weeks.
- Any Grade 5 toxicity.

Complete response (CR) rate: defined as the proportion of response-evaluable participants (see Section 12.2) that achieve a CR after 2 cycles of PolaR-ICE therapy.

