12.1.1 Safety Lead-in

Prior to formally initiating the Phase 2 response assessment, a patient safety lead-in portion will be conducted to ensure there are no unexpected toxicities with PolaR-ICE salvage therapy. The decision to open to Phase 2 will primarily be based on the number of safety lead-in patients experiencing unacceptable toxicities during the first 2 cycles of PolaR-ICE salvage, but will also take into consideration other data available at the time of decision making, including toxicities observed in cycle 3, the ability to

proceed to transplant after PolaR-ICE and delays due to study treatment-related toxicity between PolaR-ICE and transplant. The unacceptability toxicities are defined in Section 11.2. Patients evaluable for unacceptable toxicities during the Safety Lead-in are defined in Section 12.2.

During the safety lead-in portion of the study, a design that is slightly modified from the IQ rolling 6 design will be used.[7] In this design, up to 8 evaluable patients may be treated at each dose level, and the highest dose level with <33% evaluable patients having unacceptable toxicities will be considered tolerable with respect to unacceptable toxicities. Given the expected safety profile of PolaR-ICE, we adopt this design which may allow up to 6 patients at risk at any time instead of some other designs which allow up to 3 at risk. The rules of the proposed design are outlined below.

- 1) When there is no patient with unacceptable toxicities, accrual can continue for up to 8 patients with up to 6 patients at risk (i.e., under unacceptable toxicity observation) at the same time.
- 2) If there is no DLT in 5+ evaluable patients with no others at risk, (i.e., 0/5, 0/6, 0/7, or 0/8), the current dose level will be considered tolerable.
- 3) After 1 patient with unacceptable toxicity is reported, accrual can continue to up to 6 patients (i.e. <6 at risk); to accrue the 7th or the 8th patient, there must be ≤3 patients at-risk.
- 4) If there is 1 patient with unacceptable toxicity in 6-8 evaluable patients with no others at risk (i.e., 1/6, 1/7, or 1/8), the current dose level will be considered tolerable.
- 5) If there are 2 patients with unacceptable toxicities when ≤6 patients are treated, the current dose level will be considered intolerable (and dose de-escalated if at dose level 1).

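### The Section 14.5 break in AE recording can begin before Cycle 2 ends, and it leaves out related toxicity that delays transplant

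*Combined protocol and SAP*

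**What the plan says.** All references are to the combined protocol and SAP.

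- **Section 14.5** collects AEs from consent to the end of participation, "except those occurring between the end of salvage visit and the start of consolidation for subjects proceeding to HCT". The exception has no limit by attribution, grade or seriousness. The eCRF list in the same section asks for the highest grade of each toxicity per cycle, for all SAEs, and adds: "For Cycles 1 and 2 only, all Grade ≥2 AEs (highest grade or not) will also be collected".
- **Section 10, footnote h**: "End of salvage visit to occur within 30 days from last dose". No earliest day is given. The calendar schedules AE assessments on Day 1 of each salvage cycle, at End of Salvage and at Consolidation C1D1, with none between the last two. The response PET-CT is on Day 15, and footnote g says "Day 15 assessments have a ± 7 day window".
- **Section 12.1** lets a patient in CR after two cycles go straight to ASCT, so Cycle 2 can be the last salvage cycle.
- **Section 11.2** defines unacceptable toxicity, the lead-in primary endpoint, as "any of the following events occurring during the first 2 cycles of treatment that is at least possibly related to study treatment".
- **Section 12.1.1** bases the opening of Phase 2 primarily on that count. It also looks at "other data available at the time of decision making, including toxicities observed in cycle 3", and at the ability to "proceed to transplant after PolaR-ICE and delays due to study treatment-related toxicity between PolaR-ICE and transplant".
- **Section 12.6**: "Observed toxicities of PolaR-ICE salvage therapy and Pola single-agent consolidation therapy will be summarized by type", and also by severity and attribution.

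**The concern.** There are two separate problems.

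First, the lead-in endpoint needs complete recording to the end of Cycle 2. If the break opens earlier, one sentence of Section 14.5 removes events that another sentence of the same section, and Section 11.2, require. A fully dosed lead-in patient with no recorded event is still evaluable under Section 12.2 and counts as free of unacceptable toxicity. The decision rule is sensitive to single events: under Section 12.1.1, 1 of 6 is tolerable and 2 of 6 is not.

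Second, Section 12.1.1 says the team will weigh treatment-related delays before transplant. The interval in which such a delay arises is the one in which routine AE recording stops. If a new, non-serious toxicity causes the delay, the routine data need not contain the event or its attribution.

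**Working it through.** The plan gives no figure of its own on this point. The check is day arithmetic on the calendar, followed by a comparison of sections.

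**Inputs**
- Cycle length L = 21 days, 18 to 24 with the window (Section 5.2; Section 10 footnote b).
- Last scheduled salvage dose: Day 3 (Table 5.3, etoposide).
- End-of-salvage visit: up to 30 days from last dose (footnote h).
- Cycle 2 PET-CT: Day 15 ± 7, so Day 8 to Day 22 (footnote g).
- Evaluable lead-in patients: 5 to 16 (Section 5.4).
- CR rates of 40% and 60% (Section 12.1.2).

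**Step 1: when can the visit fall?** With the last dose on Day 3, footnote h allows Day 3 to Day 3 + 30 = Day 33. Cycle 2 ends on Day 21, so the break can literally start up to 21 − 3 = 18 days before the cycle ends. A more realistic assumption is that the visit follows the scan that shows CR, hence Day 8 at the earliest. The documents do not state this order.

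**Step 2: days of Cycle 2 inside the break** = max(0, L − v), where v is the cycle day of the visit.

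| Visit day v | L = 18 | L = 21 | L = 24 |
|---|---|---|---|
| 8 | 10 | 13 | 16 |
| 15 | 3 | 6 | 9 |
| 21 | 0 | 0 | 3 |

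**Step 3: can an 11.2 event fall wholly in those days?** Yes. Take a visit on Day 8 and a non-serious, related Grade 3 non-hematologic toxicity that begins on Day 12. If it has not resolved to Grade 1 by Day 12 + 7 = Day 19, it meets Section 11.2 before Cycle 2 ends, yet both dates lie in the exempt interval.

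A related case is an event open at the visit. Grade 4 neutropenia that begins on Day 7 is outside the exception by its onset. Whether it exceeds 21 days is settled only after Day 7 + 21 = Day 28, when no AE assessment is scheduled before consolidation.

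**Step 4: how many lead-in patients could be affected?** Patients in CR number between 0.40 × 5 = 2 and 0.60 × 16 = 9.6, about 10. This is a ceiling. The patient must also have no third cycle, an early visit, and a new, related, non-serious qualifying event after it. The documents give no rates for these conditions.

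**Step 5: what is kept between the visit and transplant?**
- SAEs (Section 14.5; Table 14.6)
- unanticipated problems (Table 14.6)
- AESIs, through the eCRF (Table 14.6 footnote)
- events that began before the visit
- events still present at Consolidation C1D1

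What remains unrecorded is the new-onset, non-serious, non-AESI event that resolves before consolidation. No section restores it when it is related to PolaR-ICE.

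The time from visit to ASCT is not given. After ASCT the break runs a further 30 to 60 days, or up to 75 with consultation (Section 5.7). If half of patients reach ASCT, as Section 2.1.1 reports for the reference trial, about 0.50 × 40 = 20 patients have such an interval; the ceiling is 40. These are patients with an interval, not events lost. The number of events lost cannot be derived from the documents.

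**The case against.** The exception is a deliberate and sensible choice. Mobilization, collection and ASCT follow institutional standards, and routine recording of non-serious transplant toxicity would add confounded noise. The serious outcomes stay covered, including collection failure and 100-day non-relapse mortality under Section 12.4. This stands, and it is why the exclusion of other non-serious peri-transplant events should remain.

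On Cycle 2, a salvage cycle lasts 21 days and the calendar places End of Salvage after the cycle columns. An early visit needs a scan, a reading, marrow confirmation where applicable and a decision against a third cycle, all within days. One can also argue that the specific Cycle 1 and 2 line overrides the general exception: Table 13.3 has a dedicated row for AE forms in lead-in Salvage Cycles 1 and 2, triggered by notification as well as by assessment. This makes the overlap uncommon and turns it into a conflict in the text, not a clean gap. It does not resolve the conflict, because Section 14.5 does not say which rule yields.

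On delays, Section 12.1.1 treats them as other available data, and the Protocol Management Team can discuss a delay without an AE form. That is fair, so the input is secondary. But informal discussion leaves no routine record of the event or its attribution.

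A reader might also infer three stronger points that the documents do not support:
- **The Section 12.6 toxicity summary is defective.** Section 12.6 sets no window reaching into transplant and is consistent with recording by cycle.
- **The break never ends for a patient who is transplanted but not consolidated.** Section 5.10 makes inability to proceed with consolidation a removal criterion, Section 10 footnote i then sets a safety visit, and Section 14.5 records toxicity for safety follow-up. This case is largely covered.
- **Every possibly related AE should be recorded through transplant.** Under the Section 14.1 definition of a possible relation, many events after conditioning could qualify, which could largely undo the exception.

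**Conclusion.** The concern holds in a limited form, of minor to moderate severity. The calendar permits the recording break to open inside Cycle 2 for patients in CR who go to ASCT after two cycles, against two rules that need the full cycle. The sizes of 13 and 6 days rest on a 21-day cycle and on the visit following the scan. Few lead-in patients could be affected. It would be wrong to infer that the lead-in dose decision is unreliable: a single missed event could matter, but it requires several conditions together, and the Cycle 1 and 2 line may well be followed in practice.

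Separately, related toxicity that is new, non-serious and not an AESI goes unrecorded between the visit and transplant, although Section 12.1.1 names the resulting delays as a secondary input. The Phase 2 CR endpoint is not affected by either problem.

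**What to change.** Amend Section 14.5 in two places.

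1. Start the exception no earlier than the end of the last salvage cycle, whatever the date of the end-of-salvage visit. The Section 11.2 window for Cycles 1 and 2 is then always recorded in full. Add that the resolution date is recorded for any event open at the visit that could meet Section 11.2.
2. Within the exempt interval, keep recording any toxicity at least possibly related to PolaR-ICE that delays or prevents stem cell collection or ASCT.

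Leave the exclusion of other non-serious peri-transplant AEs as it is.

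The cost is protocol wording and modest extra data entry from chart review for patients going to transplant. No visit or test is added. Some mild events may still be missed because no study visit falls in the interval, and attribution after conditioning stays uncertain. Tying the second change to delayed or prevented collection or ASCT keeps that burden small.
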